### **Data Analysis Plan**

To assess the effectiveness of our randomization procedure, we used chi-square tests and ANOVAs to investigate the equivalence of possible cofounders across each of the PLUS-enrolled four site/conditions at baseline. Specifically, we examined proportional differences across demographic characteristics (race and ethnicity, sexual and gender identity, and education), and mean differences across age and baseline outcome values (alcohol severity, drug use severity, medication adherence, viral load, and CD4). Where cell sizes were too small ( $n < 5$ ) to permit chi-square tests, we utilized a Fisher's exact test, at  $p < .05$ . The matching of the No Treatment control group ( $N = 120$ ) was assessed by bivariate comparisons with the entire PLUS-enrolled sample ( $N = 174$ ) on the available variables of age, race and ethnicity, and gender.

We also conducted analyses to test for the presence of differential attrition between conditions and sites where appropriate. First, we conducted chi-square analyses to test for differential attrition by site and study arm at each follow-up. We also tested for differential attrition at each follow-up across site, as well as several demographic characteristics (race and ethnicity, sexual and gender identity, and education). Finally, we conducted a series of point-biserial correlations to examine attrition at each wave by age and baseline outcome values (alcohol severity, drug use severity, medication adherence, viral load, and CD4).

Outcome analyses were conducted using piece-wise longitudinal growth curve models, adjusting for baseline scores on the corresponding outcome and, for the models predicting medication adherence, AUDIT, and DAST, we also adjusted for gender identity and sexual orientation, whereas for the models predicting viral load and CD4 we adjusted for gender (male, female) as sexual identity was not indicated in the EMR records for the matched cohort. For the

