DAST model, DAST was treated as a count variable having a negative binomial distribution. The latent intercept represented the initial 3-month follow-up time point. Slope 1 quantified linear change across the 3-, 6-, 9- and 12-month follow-ups. Where possible for outcomes variables extracted from EMR (i.e., CD4 count and viral load), Slope 2 quantified changes in trajectory at the 15- and 18-month follow-up corresponding to the point at which the waitlist control condition received the intervention. The fixed effect of clinic and condition was entered as a 4-category predictor that was dummy-coded. For viral load and CD4 models – where data were taken from EMR records – the EMR cohort control participants were included as an additional subgroup and served as the referent category.

All models were estimated using full-information maximum likelihood estimation in MPlus Version 8.0. Good model fit was assumed when the  $\chi^2/df$  ratio was 3 or less, root-mean square error of approximation (RMSEA)  $\leq 0.05$ , Tucker-Lewis fit index (TLI)  $> 0.95$ , and comparative fit index (CFI)  $> 0.95$ .

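### Attrition is tested against many baseline variables with no stated use of the results, and the self-report FIML models omit most of those variables

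*Combined protocol and SAP*

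**What the plan says.** All the relevant text is in the Data Analysis Plan of the combined protocol and SAP.

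**Attrition tests.** The purpose is given as: "We also conducted analyses to test for the presence of differential attrition between conditions and sites where appropriate". Three sets of tests are then listed. By group: "First, we conducted chi-square analyses to test for differential attrition by site and study arm at each follow-up". By demographics: "as well as several demographic characteristics (race and ethnicity, sexual and gender identity, and education". By age and baseline values: "we conducted a series of point-biserial correlations to examine attrition at each wave by age and baseline outcome values". Those baselines cover drinking, drug use, adherence, viral load and CD4.

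**Outcome models.** Each growth model is described as "adjusting for baseline scores on the corresponding outcome", with a four-category clinic/condition predictor. For adherence, AUDIT and DAST the plan adds: "we also adjusted for gender identity and sexual orientation". The viral load and CD4 models add binary gender only, and they include the record-based control cohort as the reference group.

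**Missing data.** The only statement on method is: "All models were estimated using full-information maximum likelihood estimation in MPlus Version 8.0". The plan names no auxiliary variables, states no assumption about missingness and gives no sensitivity analysis. It does not say how an attrition result would affect a model.

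**The concern.** FIML gives valid estimates when missingness is random given the variables in the model. The plan identifies a list of possible dropout predictors, tests them, and then fits models that contain only some of them. Any omitted variable that also predicts the outcome is information about the missing values that the model does not use.

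This matters most for AUDIT and VAS adherence, which are primary outcomes under Measures, and for DAST, which is secondary. All three are self-reported at study assessments, so a missed assessment loses the value. Dropout that depends on condition is plausible here:

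- Conditions were assigned by site, and one site changed from waitlist to immediate treatment part-way through (Trial Design).
- Immediate participants had therapy visits with travel cards from the start (Compensation), while waitlist participants waited 12 months.
- Eligibility was later widened to illicit drug use (Inclusion Criteria). Drug severity may therefore vary widely among participants in the AUDIT model, which does not contain baseline DAST.

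**Working it through.** The documents give no attrition rate, power or effect size, so there is no figure of the plan's own to reproduce. The main check compares two lists. The calculations after it are illustrations.

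**1. Variables tested for attrition against variables in the self-report models**

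| Tested for attrition | In the AUDIT, VAS and DAST models? |
|---|---|
| Site, arm | Yes, as clinic/condition |
| Gender identity, sexual identity | Yes |
| Baseline of the same outcome | Yes |
| Baselines of the other four outcomes | No |
| Age | No |
| Race/ethnicity | No |
| Education | No |

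**2. Can the attrition tests show that the omitted variables are harmless?** N = 174 is from the plan. The 0.05 level is assumed, because the plan states it only for the baseline comparisons.

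- *Correlations.* Power = Φ(atanh(r)·√(N−3) − 1.96), with √171 = 13.08. For r = 0.10: Φ(1.31 − 1.96) = 26%. For r = 0.15: Φ(1.98 − 1.96) = 51%. For 80% power, r = tanh((1.96 + 0.84)/13.08) = 0.21.
- *Difference in attrition between groups.* Group sizes are not given. Assume 44 against 130, with 20% against 30% attrition. The pooled rate is (8.8 + 39)/174 = 0.275. The null SE is √(0.275·0.725·(1/44 + 1/130)) = 0.0779. The alternative SE is √(0.16/44 + 0.21/130) = 0.0725. Power = Φ((0.10 − 1.96·0.0779)/0.0725) = 23%. With a smaller group of 30 to 87 and a base rate of 20% to 30%, power for a 10-point difference is 16% to 33%.
- *Chance findings.* Twelve variables (site, arm, race/ethnicity, sexual identity, gender identity, education, age, five baselines) at six follow-ups make 72 tests. At 0.05 that gives 3.6 expected false positives.

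The tests are thus a poor guide to which variables matter, whichever way they fall.

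**3. Size of bias (every parameter is assumed).** X is an omitted standard-normal baseline variable and the e terms are independent standard normals:

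- Y0 = 0.3X + √0.91·e0
- Y3 = 0.5·Y0 + bX + 0.8·e1
- Y12 = 0.4·Y0 + 0.4·Y3 + bX + 0.8·e2, with no true arm effect
- logit P(Y12 missing) = −1 + gX, with g set separately for each arm

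This gives 27% to 29% dropout. The likelihood-type estimate regresses Y12 on arm, Y0 and Y3 (with or without X) in those observed and predicts Y12 for everyone. It then takes the arm coefficient adjusted for Y0 and divides by the SD of Y12. With 400,000 simulated subjects the bias in SD units is:

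| g in the two arms | b | Without X | With X |
|---|---|---|---|
| any of the three patterns below | 0 | within 0.003 of 0 | within 0.003 of 0 |
| 0.7, 0.7 (same) | 0.2; 0.4 | 0.003; −0.003 | 0.003; −0.003 |
| 0.7, 0 (one arm) | 0.2; 0.4 | 0.027; 0.042 | −0.001; 0.000 |
| 0.7, −0.7 (opposite) | 0.2; 0.4 | 0.052; 0.095 | −0.006; 0.006 |

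The result depends on the set-up. A generalised-least-squares version with 28% to 44% dropout gave 0.015 to 0.03 SD (one arm) and 0.03 to 0.06 SD (opposite). Re-running the two-wave set-up with intercept −0.35, which gives about 42% dropout, gave 0.04 to 0.06 SD and 0.08 to 0.13 SD. About 0.02 to 0.05 SD, and up to about 0.10 SD for opposite relations, is a fair central range and only an order of magnitude.

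**4. Scale against sampling error.** With the assumed 44/130 split and 27% dropout, the SE of a 12-month contrast before baseline adjustment is √(1/(44·0.73) + 1/(130·0.73)) = 0.20 SD. With 44% dropout (0.56 retained) it is 0.23 SD. A bias of 0.02 to 0.05 SD is then 0.02/0.23 = 0.09 to 0.05/0.20 = 0.25 standard errors.

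**The case against.** FIML is an accepted primary method, and these models already condition on the outcome's own baseline, the earlier waves and clinic/condition. Auxiliary variables and delta adjustment are robustness additions. The illustrated bias is a fraction of a standard error and would seldom change a conclusion. It is about zero when dropout depends on the variable equally in both arms, or when the variable adds nothing to prediction of the outcome. All of this stands, and it is why the point is an improvement and not a fatal flaw. It does not explain why variables examined as dropout predictors are left out when including them costs so little.

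A reader might also infer stronger points that the documents do not support:

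- *The attrition results were never used.* Clinic/condition, own baseline, and gender and sexual identity are both tested and modelled. The plan gives no reason for choosing those covariates, so only the absence of a stated use can be claimed.
- *Missing at random should have been checked.* It cannot be verified from observed data. The real gap is the lack of auxiliary variables and of a sensitivity analysis.
- *The plan treats a non-significant attrition test as permission to ignore dropout.* It states no such rule. The power figures show only that the tests should not decide which variables to include.
- *All primary outcomes through month 18 are affected.* The slope for months 15 and 18 is reserved for outcomes taken from medical records, and viral load and CD4 are not lost merely because a study assessment is missed.

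**Conclusion.** The point holds for the AUDIT, VAS adherence and DAST models over months 3 to 12. The omission can be read directly from the text. Bias in the contrast between conditions needs three things together: the omitted variable predicts dropout, it predicts the outcome beyond what is already modelled, and its relation to dropout differs by condition. Under the assumed inputs (log-odds 0.7 per SD of the variable, coefficient 0.2 to 0.4, roughly 26% to 42% dropout) the bias is about 0.02 to 0.05 SD when the relation exists in one arm only, and up to about 0.10 SD when the relations are opposite. Whether any such bias occurred, and how large it was, cannot be judged, because the documents give neither attrition rates nor test results. The SD figures are for a continuous outcome and do not carry over directly to the DAST count model.

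**What to change.** **Self-report models.** Whatever the attrition p-values, include age, race/ethnicity, education and the other outcomes' baselines as FIML auxiliary variables in the AUDIT and VAS models, and as covariates in the DAST count model. State the missing-at-random assumption given this set, and report retention by wave and condition.

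**Sensitivity analysis.** For the primary self-report outcomes, add a delta-adjusted analysis: shift the values missing after dropout over a range, allow the shift to differ by condition, and report the point at which the conclusion changes.

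**Viral load and CD4.** Add only age and race/ethnicity. The reference group is 120 control patients known from records alone. The plan lists age, race/ethnicity and gender as the variables available for comparing them with participants, and nothing in the documents shows education, AUDIT, DAST or VAS for them.

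**Cost.** The variables are already collected, and no new participants or visits are needed. The additions mean a little more analysis and reporting, and should be labelled as supplementary if the main models have already been run. With N = 174 the auxiliary list may have to be trimmed if a model does not converge, and any trimming should be reported.

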**Aim 4: Collect and analyze retrospective cohort data and prospective natural history data, via Electronic Medical Records (EMR) at the SCCH clinics.** We aimed to conduct retrospective cohort analyses to compare virologic, immunologic, medical outcomes, and adherence to medical appointments/engagement in care between those who do (n = 1505) and do not (n = 3692) meet diagnostic criteria for alcohol abuse/dependence. We aimed to use the third SCCH clinic (which will not receive any intervention) as a natural history comparison group, and conduct prospective analyses of data to better understand the natural history of the intersection between problematic alcohol use and HIV medication adherence and HIV health outcomes. Of particular focus were analyses of potential differences by age, race/ethnicity, gender, sexual identity, viral hepatitis co-infection, years living with HIV, and years on ART.

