## **Trial Design**

This study utilized a CET design to evaluate the effectiveness of the PLUS intervention components against a waitlist condition, and for VL and CD4, against a No-Treatment control group. Four sites were distributed across three study conditions in a quasi-experimental design. Two sites (Sites 1 and 2) implemented immediate treatment (Condition 1). Immediately after baseline, participants were offered the PLUS intervention. Participants then completed follow-up assessments at 3, 6, 9, 12, 15 and 18 months post-baseline. Site 3 implemented both the waitlist condition (Condition 2) from March 26, 2015 to October 31, 2016, and an immediate condition. Due to challenges in participant accrual, this site shifted to enrolling participants in the immediate intervention condition from November 1, 2016 through the end of the study. Participants in the waitlist condition received the intervention following completion of their 12-month follow-up. Site 4 is the no-Treatment Control EMR Group.

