## **METHODS: Participants, Interventions and outcomes**

### **Inclusion Criteria**

- 18 years of age or older
- HIV-positive
- Currently receiving ART
- Current VL >200 copies/ml
- Report drinking at hazardous levels, operationalized as exceeding 14 standard drinks per week for men or exceeding 7 standard drinks per week for women, as per NIAAA guidelines. In a later amendment, criteria were expanded to also include reported use of illicit drugs exclusive of marijuana or illicit use of prescription opioids within the past 3 months.
- Must be a current patient at the clinic with current lab results

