### **Enrollment in Immediate and Waitlist control conditions**

Potential participants in the immediate and waitlist control conditions were identified through a prescreening review of EMR, which provided study staff members with lists of patients with scheduled clinic visits who had one or more detectable viral load within the past year. Study staff approached these patients during clinic visits to introduce PLUS and invited them to participate in screening. Participants provided verbal consent for screening and provided written informed consent if they were eligible and interested in enrolling. They also granted permission for the study team to abstract their EMR data for study screening and enrollment purposes.

Once consent to use the EMR was granted, eligibility criteria were verified for ART regimen and viral load. Participant self-report was used to determine alcohol and substance use criteria on the screening questionnaire. Eligible participants who enrolled in the study were scheduled for a baseline visit, which could take place the same day post-screening or be scheduled within the ensuing month. The full protocol was approved by the institutional review boards at Hunter College and Mt Sinai.

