## **MEASURES**

### *Primary Outcome Measures*

- Biological Marker of HIV-Related Health Outcomes
  - Viral load and CD4 extracted from EMR
- Alcohol Use
  - Alcohol Use Disorders Identification Test (AUDIT)
  - Hazardous Drinking
- Medication Adherence
  - Visual Analog Scale (VAS) for Medication Adherence

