## **Selection of No Treatment control patients**

The EMRs of randomly selected patients who belonged to the TAU site and were not enrolled in the PLUS trial were matched on key patient characteristics for comparisons with EMRs of patients in the PLUS intervention and Waitlist control conditions. This matched cohort of patients received care at a fourth clinic that did not receive any intervention (i.e., PLUS or eTAU) and was considered as a natural history comparison group. We generated a pool of patient records from which to randomly select the TAU matched cohort of patients ( $n = 120$ ). We included patient records of patients with an HIV diagnosis who had at least 1 primary care visit at the TAU clinic, received ART, and had a viral load (VL)  $>200$  copies/mL during the PLUS enrollment period from March 26, 2015 to March 16, 2017. EMRs of 20 patients who were enrolled in PLUS and possibly transferred to receive HIV care at the TAU clinic during the study period were excluded. Additionally, records of 9 patients with only one primary care visit and no follow-up visits during the study period were excluded from the pool of patient records.

Case control matching using the pool of patients meeting the criteria described above allowed us to randomly select the TAU cohort of 120 patients while matching as closely as possible to patients enrolled in the trial on key variables: age group (with ranges 18-29, 30-39, 40-49, and 50 or older), racial and ethnic identity (Black, Hispanic/Latinx, White, Asian/Pacific Island, Other/Multiracial), and gender (recorded as male or female). Additionally, we matched on indicators of substance misuse based on EMRs of trial participants using documentation of substance use problems or ICD-10 diagnostic codes, such as documentation of alcohol abuse or dependence, having had a substance use diagnosis, or any indication of substance misuse during the study period. EMRs were then extracted for the TAU cohort of patients similar to the records

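### The viral load and CD4 models adjust non-randomised groups for one baseline value and gender; if groups differ in chronic viremia, part of that difference stays in the level contrasts, and earlier EMR results could reduce it

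*Combined protocol and SAP*

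**What the plan says.** **Allocation.** Trial Design states: "Four sites were distributed across three study conditions in a quasi-experimental design". Site 3 moved from waitlist to immediate treatment on a calendar date because of slow accrual. The Data Analysis Plan speaks of a randomisation procedure, but none is described.

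**Model.** The outcome models are described as: "Outcome analyses were conducted using piece-wise longitudinal growth curve models, adjusting for baseline scores on the corresponding outcome". The further covariate for the two EMR outcomes is gender: "for the models predicting viral load and CD4 we adjusted for gender (male, female"). Clinic and condition enter as dummy-coded categories, with the EMR cohort as referent for VL and CD4. The intercept is the 3-month value, Slope 1 covers months 3 to 12, and Slope 2 covers months 15 and 18. No earlier value, duration of viremia, propensity score or weighting is mentioned.

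**Entry rules.** Trial patients need "Current VL >200 copies/ml". EMR controls need a VL above 200 "copies/mL during the PLUS enrollment period from March 26, 2015 to March 16, 2017". No baseline or index date is given for controls.

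**Matching.** Controls were matched on age group, race/ethnicity, gender and substance misuse. The match (120 against 174) was checked on age, race/ethnicity and gender. VL history and CD4 are in neither list.

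**Earlier results.** Prescreening listed patients "who had one or more detectable viral load within the past year". Aim 4 is to "Collect and analyze retrospective cohort data and prospective natural history data, via Electronic Medical Records (EMR) at the SCCH clinics". Both primary biological outcomes have the same source: "Viral load and CD4 extracted from EMR".

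**The concern.** Two patients with the same entry VL may differ greatly in outlook: one is viremic at nearly every test, the other had a single detectable result. One truncated measurement separates them poorly. Without randomisation, nothing in the design balances the mix of such patients across groups. The entry rules also differ: a current value above 200 in the trial, any value above 200 over about two years for controls.

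Adjusting for one noisy measurement removes only part of a true difference in long-run level. The remainder would be read as benefit or harm from PLUS, on primary outcomes that are also the only ones compared with the no-treatment group. Earlier laboratory results that could reduce the remainder lie, at least in part, in a record system the study already uses.

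**Working it through.** The documents give no variance, effect size or power for these outcomes, so there is no figure to reproduce. All numerical inputs below are assumptions, apart from the group sizes 174 and 120 and the threshold of 200 copies/ml.

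**1. Closed form.** Let rho be the share of the variance of one measurement that is due to the patient's long-run level. After adjusting for the entry value and k earlier values, the share of a true group difference left in the contrast is (1 - rho)/(1 + k x rho).

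| rho | entry value only (k = 0) | plus three earlier values (k = 3) |
|---|---|---|
| 0.3 | 0.7/1 = 70% | 0.7/1.9 = 37% |
| 0.5 | 0.5/1 = 50% | 0.5/2.5 = 20% |
| 0.7 | 0.3/1 = 30% | 0.3/3.1 = 10% |

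**2. Two viremia classes, no PLUS effect.** Persistent patients exceed 200 on about 82.5% of draws and the others on about 32.5%. All exceed 200 at entry, and the level above 200 carries no information on class, which is the unfavourable end. The 174 are split 120 immediate and 54 waitlist (assumed). The outcome is mean log10 VL over months 3-12.

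- A 15-point imbalance (65% against 50% persistent) shifts the detectable share by 0.15 x (0.825 - 0.325) = 0.075. With about 2.4 log10 between an average detectable and an undetectable value, the bias is 0.075 x 2.4 = 0.18.
- The standard error is about 0.133, so 0.18/0.133 = 1.35 and the normal false-positive rate is about 27%. Simulation gives about 26%.
- Adding the share of three earlier VLs above 200 leaves about 0.09 with a standard error of about 0.116. Then 0.09/0.116 = 0.78, or about 12%. Simulation gives 12-13%.
- A 5-point imbalance: 0.05 x 0.50 x 2.4 = 0.06; 0.06/0.133 = 0.45, or about 7%.
- Equal groups: no bias, and the standard error falls by 1 - 0.116/0.133 = 13%.
- Weaker persistence (70% against 40% of draws): history removes only about 20% of the bias and 2% of the standard error. Under a pure AR(1) process it adds nothing.

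**3. Which parameter is affected.** A stable class shifts all of a patient's follow-up values by the same amount, so the shift cancels in a slope. Simulated Slope 1 (months 3-12) at the 15-point imbalance has bias 0.00 and 5% false positives, with or without history. The month-3 value alone carries the same bias as the mean but is noisier, so its false-positive rate is about 11-14%. A straight-line intercept at month 3 weights the four visits 0.7, 0.4, 0.1 and -0.2. Its squared weights sum to 0.70, against 1 for month 3 alone and 0.25 for the mean, so its rate falls between those two.

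**4. A mixture in which the entry level is informative.** Groups of 174 and 120; long-run log10 VL is Normal(4.0, SD 0.6) in chronic and Normal(1.8, SD 0.4) in transient patients, with within-patient SD 0.7. Chronic shares of 50% and 30% in the source become 78% and 61% after selection above 200. The null difference is 0.33 unadjusted, 0.16 with the entry value and 0.04 with the mean of three earlier values. False positives are 42% with the entry value alone and 12% with history added. With equal shares both are about 5%.

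**The case against.** **The imbalance is assumed.** No section shows that groups differ in chronic viremia, or in which direction. Immediate and waitlist patients share one entry rule, Site 3 supplies both, and baseline VL and CD4 are compared across the trial cells. This stands: the illustration shows what could happen, not what did.

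**Not every contrast is affected.** A reader might infer that all PLUS contrasts inherit the problem. The plan fits an intercept and slopes, and a stable difference in level does not bias Slope 1. This stands.

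**Pooling flatters the error rates.** The model uses separate clinic/condition cells. At an assumed 40 per cell, the 15-point imbalance gives 19% against 54 waitlist patients and 21% against the 120 controls, rather than 26%. This stands, but both remain well above 5%.

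**The entry value is not useless.** It is tempting to say that an entry VL above 200 cannot identify chronic viremia at all, or that selecting on it biases the regression. Neither holds. In the mixture, adjusting for it halves the difference (0.33 to 0.16), and truncation alone does not bias a correctly specified linear regression on that value. The weakness is one range-restricted measurement.

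**History may be missing.** A reader might infer that earlier results are held for every patient. The text shows a one-year look at prescreening and a retrospective Aim 4, but states no look-back for the extracted dataset. Some controls may have few earlier values.

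**CD4 was not simulated.** CD4 was not an entry criterion, so the truncation argument does not apply to it. Only the closed form in step 1 carries over.

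**Conclusion.** The point holds as a conditional one. The VL and CD4 models rely on one baseline value and gender to make non-randomised groups comparable, and neither the matching nor its check covers VL or CD4 history. If groups differ in chronic viremia, part of the difference stays in the level contrasts: 30-70% of it for rho from 0.7 to 0.3, or about 0.18 log10 with about 26% false positives for the months 3-12 mean at a 15-point imbalance. At 5 points the rate is about 7%.

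These sizes rest on assumed persistence, imbalance and group sizes. The Slope 1 result rests on stable classes. The documents do not support the stronger conclusion that the planned PLUS contrasts are in fact biased, because they give no viremia history by group. Earlier results would reduce the exposure but not remove it, and where viremia is strongly persistent they would also improve precision when groups are balanced.

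**What to change.** 1. Define an index date for the EMR controls. Without it, neither baseline nor history has a meaning in the reference group.
2. Extract VL and CD4 over a fixed look-back before baseline or index (for example 12 months) in all groups, where available.
3. Report this history by group in the baseline table, including the number of earlier results.
4. Add to the VL model the share of earlier VLs above 200 and the mean earlier log10 VL, excluding the qualifying value. Add mean earlier CD4 to the CD4 model, for precision and general confounding control. Include the number of earlier results or a no-history indicator in both.
5. Keep the single-baseline model as a sensitivity analysis.

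The cost is SAP wording and a further laboratory pull from the EMR. As the analysis dataset is described as de-identified, relinking may be needed. History will be sparse for some patients, and site differences confounded with condition will remain.

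### A gap in the EMR cohort's records also limits covariate adjustment of PLUS versus waitlist on viral load and CD4, where the trial holds the missing variables

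*Combined protocol and SAP*

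**What the plan says.** All outcome models in the Data Analysis Plan adjust for the baseline value of their own outcome. Beyond that, two covariate sets are used:

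- For adherence, AUDIT and DAST: "we also adjusted for gender identity and sexual orientation".
- For viral load and CD4: "we adjusted for gender (male, female) as sexual identity was not indicated in the EMR records for the matched cohort".

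In the viral load and CD4 models, "the EMR cohort control participants were included as an additional subgroup and served as the referent category". It joins the four clinic/condition cells of the enrolled sample.

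The Trial Design section sets out two comparisons. The study is to "evaluate the effectiveness of the PLUS intervention components against a waitlist condition, and for VL and CD4, against a No-Treatment control group". The Primary Outcome Measures list includes viral load and CD4.

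The enrolled participants' data do contain the variables at issue. In the baseline equivalence checks across the enrolled cells, "we examined proportional differences across demographic characteristics (race and ethnicity, sexual and gender identity, and education" among others. The attrition checks use the same characteristics.

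**The concern.** The missing variable is a property of the EMR cohort alone. It is a sound reason to leave sexual identity out of contrasts with that cohort. It is no reason to leave it out of PLUS versus waitlist, which involves only enrolled participants. Because all five groups share one model, the limitation carries over to a comparison it does not concern.

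This matters because the design is quasi-experimental: condition followed clinic and, at Site 3, calendar period. Measured covariates are therefore one of the few protections the PLUS-versus-waitlist contrast has. As planned, that contrast is adjusted one way for AUDIT and adherence and another way for viral load and CD4, in the same people and the same cells. If the biological and self-report results disagreed, the difference in covariates would be one possible explanation that the plan could not exclude.

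**Working it through.** The plan states no figure on this point, so there is none to reproduce. The check sets the text of the two model families side by side and then adds a bounded illustration.

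**Covariate sets (Data Analysis Plan)**

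| | Adherence, AUDIT, DAST | Viral load, CD4 |
|---|---|---|
| Own baseline | yes | yes |
| Gender | gender identity | male/female |
| Sexual orientation | yes | no |
| Groups in model | 4 enrolled cells | 4 enrolled cells + EMR cohort |
| EMR cohort as referent | no | yes |

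The binary gender coding matches the way gender is recorded in the EMR (Selection of No Treatment control patients).

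**Who lacks the variable.** Enrolled sample 174, EMR cohort 120, both from the Data Analysis Plan.
- Pooled sample: 174 + 120 = 294.
- EMR cohort, without sexual identity: 120/294 = 40.8%.
- Enrolled participants: 174/294 = 59.2%.

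**How PLUS versus waitlist is obtained.** With the EMR cohort as referent, each dummy coefficient compares one enrolled cell with that cohort. PLUS versus waitlist is then a difference between dummy coefficients, which the plan does not write out. No viral load or CD4 model limited to enrolled participants is described, and no sensitivity analysis with the fuller covariate set.

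**Possible size (assumed inputs).** The documents give neither the distribution of sexual orientation by cell nor its association with viral load or CD4. For one omitted binary covariate,

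bias in SD units = (association with outcome, in SD) × (difference in prevalence between PLUS and waitlist).

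Assume an association of 0.1 to 0.5 SD and a prevalence difference of 0 to 30 percentage points:
- no prevalence difference: 0
- 0.1 × 0.30 = 0.03 SD
- 0.2 × 0.10 = 0.02 SD
- 0.3 × 0.20 = 0.06 SD
- 0.5 × 0.30 = 0.15 SD

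**Effect of the baseline adjustment already planned.** Suppose the covariate relates equally to the baseline and follow-up values, the two have equal variance, and their within-group correlation is r. The remaining bias is then about (1 − r) times the figure above. For the largest corner:
- r = 0.3: 0.15 × 0.7 = 0.105 SD
- r = 0.5: 0.15 × 0.5 = 0.075 SD
- r = 0.7: 0.15 × 0.3 = 0.045 SD

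The documents do not give r. The range therefore runs from nothing to modest.

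**The case against.** The best defence is that the plan discloses the reduced adjustment and gives its reason, and that one common covariate set in a pooled model is conventional. The plan offers no rationale linking sexual orientation to viral load or CD4; relevance to self-reported drinking, drug use and adherence does not establish relevance to laboratory values. Race and ethnicity, education and age also appear among the possible confounders checked at baseline, yet no outcome model adjusts for them, so being on that list does not make a variable essential. Baseline adjustment may absorb part of any imbalance.

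Most of this stands, and it limits how strongly the point can be put. It does not remove it: the only reason given for the omission is missing data in a group outside the PLUS-versus-waitlist contrast.

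Four stronger readings are tempting, and the documents do not support them.
- That gender is removed from the biomarker models. It is kept in coarser form; only sexual orientation is dropped.
- That every other primary outcome has the fuller adjustment. It is stated for adherence, AUDIT and DAST. DAST is secondary, and Hazardous Drinking is listed as primary with no model stated. The documented contrast is two primary outcomes against two.
- That the false-positive rate is materially inflated. This would need cell sizes, prevalences and associations that the documents do not report, and a simple two-group calculation would ignore both the baseline adjustment and the growth-curve structure.
- That viral load and CD4 are also short-changed by using only their own baseline. That is the rule for all the outcome models and has nothing to do with pooling.

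**Conclusion.** The point holds as a limited and avoidable weakness. Pooling the EMR cohort applies a reduced covariate set to PLUS versus waitlist on two primary outcomes, although the trial collected the fuller set and uses it in three other models of the same non-randomised cells. The consequences are a possible source of confounding that need not be left open, and estimates of one contrast that are not adjusted alike across outcomes.

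The illustrative bias is 0 to 0.15 SD before baseline adjustment and smaller after it under the equal-association assumption. Its direction is unknown and it may be nil. That the two variables are complete for all 174 participants is inferred from their use elsewhere in the plan, not stated. The contrasts with the EMR cohort are not at issue, since there the restriction is unavoidable.

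**What to change.** Add one viral load model and one CD4 model in the 174 enrolled participants only, with the waitlist cell as referent. Adjust for the outcome's own baseline, gender identity and sexual orientation, as in the adherence, AUDIT and DAST models, and take PLUS versus waitlist from these. This also makes the comparison of each PLUS cell with waitlist a direct coefficient. Keep the pooled model with male/female gender for contrasts with the EMR cohort, and say which model serves which comparison.

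The cost is one extra run per biomarker and a few more parameters, with no new data collection. It requires participants' survey responses to be linked to their EMR outcomes; the plan does not describe this link in so many words. Some identity categories may be sparse (the plan itself expects cells below 5 in its baseline tables), so the rule for collapsing them should be stated and applied to all the models that use these variables.
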